#### **3.2.4 Patient's Assessment of Arthritis Pain**

Subjects will assess the severity of their current arthritis pain using a continuous visual analog scale (VAS) with anchors “0” (no pain) and “100” (most severe pain).

No imputations for missing data will be done.

#### **3.2.5 Patient's Global Assessment of Disease Activity**

Subjects will complete a global assessment of disease activity using the patient global assessment of disease activity (PtGA) item, a continuous VAS with anchors “0” (very well) to “100” (very poor).

No imputations for missing data will be done.

#### **3.2.6 Physician's Global Assessment of Arthritis**

Physicians will complete a global assessment of disease activity using the physician global assessment of disease activity item (PhGA), a continuous VAS with anchors “0” (none) to “100” (extremely active).

No imputations for missing data will be done.

#### **3.2.7 SDAI**

The Simple Disease Activity Index (SDAI) is a composite score consisting of the sum of SJC28, TJC28, PtGA/10, PhGA/10, and CRP (mg/dl). Higher values represent higher disease activity.

If one of the components is missing at an individual assessment point, the SDAI value for that assessment will be set to missing.

#### **3.2.8 CDAI**

The Clinical Disease Activity Index (CDAI) is a composite score consisting of the sum of SJC28, TJC28, PtGA/10, PhGA/10. CDAI ranges from 0 to 76 with higher values representing higher disease activity. Remission is achieved for a non-missing CDAI value  $\leq 2.8$ .

If one of the components is missing at an individual assessment point, no imputations will be done and the CDAI value for that assessment will be set to missing.

### 3.2.9 Index- and Boolean-based ACR/EULAR Remission Rates

Boolean-based remission ([Felson, 2011](#)) is achieved if all of the following requirements are met at the same time:

- $TJC68 \leq 1$
- $SJC66 \leq 1$
- $CRP \leq 1\text{mg/dl}$
- $PtGA \leq 10$

If one of the components is missing at an individual assessment point, Boolean-based remission for that assessment will be set to missing.

Index-based remission is achieved if the following requirement is met:

- $SDAI \leq 3.3$

If the SDAI value is missing at an individual assessment point, Index-based remission for that assessment will be set to missing.

### 3.2.10 HAQ-DI

The functional status of the subject will be assessed by means of the Disability Index of the Stanford Health Assessment Questionnaire (HAQ-DI). This 20-question instrument assesses the degree of difficulty a person has in accomplishing tasks in eight functional areas:

- dressing & grooming, rising, eating, walking, hygiene, reach, grip, and common daily activities.

Each functional area contains at least two questions. For each question, there is a four level response set that is scored from 0 (without any difficulty) to 3 (unable to do). If aids or devices or physical assistance are used for a specific functional area and the maximum response of this functional area is 0 or 1 the according value is increased to a score of 2.

Aid or equipment	Will be associated with category score
Walking stick/frame, crutches, wheelchair	Walking
Aids used for dressing	Dressing and grooming
Specially adapted utensils	Eating
Specially adapted chair	Rising
Raised toilet seat, bath rail, bath seat	Hygiene
Long-handled appliance in bathroom	Hygiene
Long-handled appliance for reaching	Reach
Jar opener	Grip
Other (1)	Dressing & grooming, rising, eating, walking

Other (2)	hygiene, reach, grip, common daily activities
-----------	---

If “other” is marked as an aid or equipment then this can be assigned to a group of four functional areas and will be handled as an aid or equipment for each of the four functional areas. Therefore, if the maximum score of a functional area is 0 or 1 that value is increased to a score of 2 for each of the four functional areas.

Regarding these corrections, the highest response within each functional area determines the score of that specific functional area. If no questions within a given functional area were answered, no score will be provided for that category (even if answers on aids or equipment are available).

HAQ-DI is only calculated if there are at least 6 functional area scores available.

The average of these non-missing functional area scores defines the continuous HAQ-DI score ranging from 0 to 3. If there are less than 6 functional area scores available, no imputation will be done and the HAQ-DI will be set to missing for the according assessment.

Severity of pain within the past week is also assessed by the HAQ-DI questionnaire but will not be considered for calculating the HAQ-DI score. Severity of pain will not be included in summaries but will be listed.

### 3.2.11 Short-Form 36

Health-related quality of life will be assessed using the subject-completed Medical Outcomes Study Short-Form 36 (SF-36) which is a generic health survey that contains 36 questions covering eight domains of health. The SF-36 yields an eight-scale profile of functional health and well-being scores as well as physical and mental component health summary scores. The version 2, 1-week recall questionnaire will be used. Recoding, calculations and standardisation will be done as recommended in the User’s manual for the SF-36 ([Maruish, 2011](#)).

#### 3.2.11.1 Domain Scores of SF-36

Each of the 8 domain scores is the sum of some of the overall 36 item scores.

Item	Abbreviated Item Content
Item 1	Health
Item 2	Health now compared to 1 week ago
Item 3a	Health limits vigorous activities
Item 3b	Health limits moderate activities
Item 3c	Health limits lifting or carrying groceries
Item 3d	Health limits climbing several flights of stairs
Item 3e	Health limits climbing one flight of stairs
Item 3f	Health limits bending, kneeling or stopping
Item 3g	Health limits walking more than mile
Item 3h	Health limits walking several hundred yards
Item 3i	Health limits walking one hundred yards

Item 3j	Health limits bathing or dressing
Item 4a	Cutting work time due to physical health
Item 4b	Accomplishing less due to physical health
Item 4c	Limited in kind of work due to physical health
Item 4d	Difficulty performing work due to physical health
Item 5a	Cutting work time due to emotional problems
Item 5b	Accomplishing less due to emotional problems
Item 5c	Less carefully due to emotional problems
Item 6	Physical health/emotional problems interfere with social activities (extent)
Item 7	Bodily Pain
Item 8	Pain interferes with work
Item 9a	Full of Life
Item 9b	Nervous
Item 9c	Down in the dumps
Item 9d	Calm and peacefully
Item 9e	Lot of energy
Item 9f	Downhearted and low
Item 9g	Worn out
Item 9h	Happy
Item 9i	Tired
Item 10	Physical health/emotional problems interfere with social activities (frequency)
Item 11a	Getting ill more easily than other people
Item 11b	As healthy as anybody
Item 11c	Expecting health to get worse
Item 11d	Excellent health

For every one of the items, the answers will be rated in a way such that higher values will be associated with higher health-related quality of life (see ratings below).

Rating of the item answers:

Item 1:

Answer	Excellent	Very Good	Good	Fair	Poor
Value	5.0	4.4	3.4	2.0	1.0

Item 2:

Answer	Much better now	Somewhat better now	About the same	Somewhat worse	Much worse
Value	1	2	3	4	5

Item 2 is not used for the calculation of any of the 8 domain scores.

Items 3a-3j:

Answer	Yes, limited a lot	Yes, limited a little	No, not limited at all
Value	1	2	3

Items 4a-4d and 5a-5c:

Answer	All of the time	Most of the time	Some of the time	A little of the time	None of the time
Value	1	2	3	4	5

Item 6:

Answer	Not at all	Slightly	Moderately	Quite a bit	Extremely
Value	5	4	3	2	1

Item 7:

Answer	None	Very mild	Mild	Moderate	Severe	Very severe
Value	6.0	5.4	4.2	3.1	2.2	1.0

Item 8 is recoded depending on whether item 7 is answered or not:

Original Answer item 8	Not at all	Not at all	A little bit	Moderately	Quite a bit	Extremely
Answer item 7	Very severe	None, Very mild, Mild, Moderate, Severe	None, Very mild, Mild, Moderate, Severe, Very severe	None, Very mild, Mild, Moderate, Severe, Very severe	None, Very mild, Mild, Moderate, Severe, Very severe	None, Very mild, Mild, Moderate, Severe, Very severe
Value item 8	6	5	4	3	2	1

Original Answer item 8	Not at all	A little bit	Moderately	Quite a bit	Extremely
Answer item 7	NA	NA	NA	NA	NA
Value item 8	6.0	4.75	3.5	2.25	1.0

Items 9a, 9d, 9e, 9h:

Answer	All of the time	Most of the time	Some of the time	A little of the time	None of the time
Value	5	4	3	2	1

Items 9b, 9c, 9f, 9g, 9i and 10:

Answer	All of the time	Most of the time	Some of the time	A little of the time	None of the time
Value	1	2	3	4	5

Items 11a and 11c:

Answer	Definitely true	Mostly true	Don't know	Mostly false	Definitely false
Value	1	2	3	4	5

Items 11b and 11d:

Answer	Definitely true	Mostly true	Don't know	Mostly false	Definitely false
Value	5	4	3	2	1

The initial domain scores are the sum of individual item scores:

General Health (GH)

$$GH = 1 + 11a + 11b + 11c + 11d$$

Physical Functioning (PF)

$$PF = 3a + 3b + 3c + 3d + 3e + 3f + 3g + 3h + 3i + 3j$$

Role Physical (RPh)

$$RPh = 4a + 4b + 4c + 4d$$

Role Emotional (RE)

$$RE = 5a + 5b + 5c$$

Social Functioning (SF)

$$SF = 6 + 10$$

Bodily Pain (BP)

$$BP = 7 + 8$$

Vitality (VT)

$$VT = 9a + 9e + 9g + 9i$$

Mental Health (MH)

$$MH = 9b + 9c + 9d + 9f + 9h$$

Imputation

Domain scores will only be calculated if less than half of the item scores are missing. Missing item scores will be imputed as the mean of the other item scores within the same domain. If at least half of the item scores of a domain are missing, imputation will not be performed and the domain will be set to missing.

Standardisation

All raw domain scores will be transformed on a 0–100 scale (transformed domain scores) and then standardised into norm-based scores:

Transformed domain score =  $100 \times (\text{Actual raw score} - \text{lowest possible raw score}) / (\text{highest possible raw score} - \text{lowest possible raw score})$

One example would be:

$$PF\_S = 100 * (PF - 10) / (30 - 10)$$

Each transformed domain score is standardised using a z-score transformation. Z-scores are computed by subtracting the health domain scale's 2009 U.S. general population mean from the

0–100 score for that scale, and then dividing the difference by the given scale's standard deviation:

$$PF\_Z = (PF\_S - 83.29094) / 23.75883$$

$$RPh\_Z = (RPh\_S - 82.50964) / 25.52028$$

$$BP\_Z = (BP\_S - 71.32527) / 23.66224$$

$$GH\_Z = (GH\_S - 70.84570) / 20.97821$$

$$VT\_Z = (VT\_S - 58.31411) / 20.01923$$

$$SF\_Z = (SF\_S - 84.30250) / 22.91921$$

$$RE\_Z = (RE\_S - 87.39733) / 21.43778$$

$$MH\_Z = (MH\_S - 74.98685) / 17.75604$$

The next step is the transformation of each z-score to a norm-based score using a t-score transformation (Mean=50, Standard Deviation (SD) =10) and the following formulas:

$$PF\_N = 50 + (PF\_Z * 10)$$

$$RPh\_N = 50 + (RPh\_Z * 10)$$

$$BP\_N = 50 + (BP\_Z * 10)$$

$$GH\_N = 50 + (GH\_Z * 10)$$

$$VT\_N = 50 + (VT\_Z * 10)$$

$$SF\_N = 50 + (SF\_Z * 10)$$

$$RE\_N = 50 + (RE\_Z * 10)$$

$$MH\_N = 50 + (MH\_Z * 10)$$

These norm-based values (e.g. PF\_N) are the final domain scores and will be used in summary tables. The raw values (e.g. PF), the standardised values (e.g. PF\_S) and the final scores (e.g. PF\_N) will be shown in a listing for every subject and visit.

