	
 
assessment timepoints.
 
• Index- and Boolean-based ACR/EULAR remission rates, and CDAI remission rate at all assessment timepoints.
 
• Change from baseline in SDAI and CDAI at all assessment timepoints.
 
• Change from baseline in HAQ-DI score at all assessment timepoints.
 
• Change from baseline in pain score at all assessment timepoints.
 
• Change from baseline in physical and mental component scores and in domain scores of SF-36 at all assessment timepoints.
 
• Change from baseline in FACIT-Fatigue at all assessment timepoints.
 
• Change from baseline in BFI Question 3 at all assessment timepoints.
 
 
Note: For composite endpoints, e.g., DAS28(CRP), ACR Response, etc., each component of the assessment will also be reported. Results over time, reflecting all assessment time points, will also be reported (e.g., graphically, as well as in Tables and Listings).
 
Major Secondary Safety Endpoints
 
 
• Incidence of adverse events and serious adverse events.
 
• Incidence of infections.
 
• Incidence of pulmonary events.
 

Exploratory
Efficacy Endpoints

 
• Proportion of subjects achieving sustained (<math>\geq 24</math> continuous weeks including Week 52) DAS28(CRP) remission.
 
• Proportion of subjects achieving Major Clinical Response (proportion of subjects achieving ACR70 for <math>\geq 24</math> continuous weeks including Week 52).
 

• DAS28(ESR) scores/responses at all assessment timepoints.

Pharmacokinetic/Pharmacodynamic Endpoints

• GSK3196165 pharmacokinetic parameters derived from serum concentration using sparse sampling.

• Pharmacodynamic biomarkers to assess target engagement (e.g., serum concentration of free GM-CSF, GM-CSF-GSK3196165 complex).

• Pharmacodynamic biomarkers which may be predictive of response to GSK3196165 (e.g. may include, but not limited to, 14-3-3<math>\eta</math>, MRP8/14, MMP-3, SAA ).

• Pharmacodynamic biomarkers to assess response to GSK3196165 (e.g. may include, but not limited to, IL-6, IL-1<math>\beta</math>, TNF<math>\alpha</math>, IL-17F, CCL17/Thymus and activation regulated cytokine ).

Safety Biomarkers

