### 3.2.11.2 Physical and Mental Component Scores

Following the transformation of the eight domain scores into z-scores, the Mental Component Summary (MCS) and the Physical Component Summary (PCS) are aggregated using weights from the 1990 US general population:

$$AGG\_PHYS = (PF\_Z * 0.42402) + (RPh\_Z * 0.35119) + (BP\_Z * 0.31754) + (GH\_Z * 0.24954) + (VT\_Z * 0.02877) + (SF\_Z * -0.00753) + (RE\_Z * -0.19206) + (MH\_Z * -0.22069)$$

$$\text{AGG\_MENT} = (\text{PF\_Z} * -0.22999) + (\text{RPh\_Z} * -0.12329) + (\text{BP\_Z} * -0.09731) + (\text{GH\_Z} * -0.01571) + (\text{VT\_Z} * 0.23534) + (\text{SF\_Z} * 0.26876) + (\text{RE\_Z} * 0.43407) + (\text{MH\_Z} * 0.48581)$$

Finally, each component score is transformed to norm-based scoring using the following formulas:

Transformed Physical Score: PCS = 50 + (AGG\_PHYS \* 10)

Transformed Mental Score: MCS = 50 + (AGG\_MENT \* 10)

Component scale scores (PCS and MCS) will be set to missing if the subject is missing any one of the eight SF-36 scales.

While the norm-based scores are calculated such that the mean  $\pm$  SD of these scores in the US general population is  $50 \pm 10$ , the lowest and highest possible scores for the PCS are 1 and 81, respectively. For the MCS, the lowest and highest possible scores are -9 and 82, respectively.

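### The SF-36 item 8 recode gives its top value only to subjects in very severe pain and denies it to pain-free subjects

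*SAP*

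**What the plan says.** SAP Section 2 lists among the major secondary efficacy endpoints: "Change from baseline in physical and mental component scores and in domain scores of SF-36 at all assessment timepoints". Table 6 of the SAP shows that these scores are analysed by repeated-measures model.

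Section 3.2.11.1 gives the general scoring rule: "the answers will be rated in a way such that higher values will be associated with higher health-related quality of life". Item 7 is scored from *None* to *Very severe* as "6.0 5.4 4.2 3.1 2.2 1.0".

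For item 8, the section says "Item 8 is recoded depending on whether item 7 is answered or not". The table for an answered item 7 has six columns, with the bottom row "Value item 8 6 5 4 3 2 1". The first two columns are both for *Not at all*. The first, with value 6, applies when item 7 is *Very severe*. The second, with value 5, applies when item 7 is "None, Very mild, Mild, Moderate, Severe". A companion table for an unanswered item 7 gives *Not at all* 6.0.

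Section 3.2.11 also says: "Recoding, calculations and standardisation will be done as recommended in the" SF-36 user's manual. It does not say which source governs if the printed table and the manual differ.

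**The concern.** For one and the same answer on interference, a subject with the worst pain gets the best value and a subject with no pain cannot get it. Item 7 itself runs the other way, with *None* at 6.0 and *Very severe* at 1.0. The two item 7 lists are exact complements and all six columns line up with their values, so this does not look like damage from reading the PDF.

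Bodily Pain is the sum of items 7 and 8, and it feeds both component scores. If the table is programmed as printed, Bodily Pain, PCS and MCS are all mis-scored. The section also prints no raw range for Bodily Pain, although the 0-100 transformation needs one. Which subjects are affected depends on the range the programmer uses.

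**Working it through.** **Inputs (SAP 3.2.11.1 and 3.2.11.2).** Item 7 values 6.0, 5.4, 4.2, 3.1, 2.2, 1.0. Item 8 values as printed. BP = item 7 + item 8. Transformed score BP_S = 100 × (BP − lowest) / (highest − lowest). BP_Z = (BP_S − 71.32527) / 23.66224. Norm-based score = 50 + 10 × BP_Z. Weight of BP_Z: 0.31754 in PCS, −0.09731 in MCS.

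**The plan's own figures.** Section 3.2.11.2 says that "the lowest and highest possible scores for the PCS are 1 and 81, respectively", and gives −9 and 82 for MCS. Setting each domain to 0 or 100 according to the sign of its weight, with BP_S running from 0 to 100, gives:

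- PCS 0.65 to 80.73, which rounds to 1 and 81
- MCS −8.81 to 81.65, which rounds to −9 and 82

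Both stated ranges reproduce, provided Bodily Pain can reach 100.

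**Attainable raw scores.** As printed, *None / Not at all* gives 6.0 + 5 = 11, the maximum. *Very severe / Not at all* gives 1.0 + 6 = 7. The minimum is 1.0 + 1 = 2. A raw score of 12 cannot occur. With the two conditions exchanged, the same two combinations give 6.0 + 6 = 12 and 1.0 + 5 = 6.

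**All 6 × 5 = 30 combinations, printed against corrected table (corrected on range 2 to 12).** The rows that show the pattern:

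| Item 7 / item 8 | Corrected, 2-12 | Printed, 2-12 | Printed, 2-11 |
|---|---|---|---|
| None / Not at all | 100 | 90 | 100 |
| Very mild / Not at all | 84 | 84 | 93.3 |
| None / A little bit | 80 | 80 | 88.9 |
| Very severe / Not at all | 40 | 50 | 55.6 |

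- Range 2 to 12: 2 of 30 combinations change, the first and last rows.
- Range 2 to 11: 28 of 30 are inflated. Only *None / Not at all* (100) and *Very severe / Extremely* (0) are unchanged. The last three rows are 3.9, 3.8 and 6.6 norm-based points too high.

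**Size per affected subject, range 2 to 12.** Ten BP_S points are 10 × 10 / 23.66224 = 4.23 norm-based points. PCS moves by 0.31754 × 4.23 = 1.34, and MCS by 0.09731 × 4.23 = 0.41 in the opposite direction. For *None / Not at all*, Bodily Pain and PCS are too low and MCS too high. For *Very severe / Not at all* the signs reverse.

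**Check against the stated limits.** With Bodily Pain capped at 90, the PCS maximum is 80.73 − 1.34 = 79.39 and the MCS minimum is −8.81 + 0.41 = −8.40. These do not match 81 and −9. On range 2 to 11 the limits do match, so they do not show which version was programmed.

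**Group difference, range 2 to 12.** The documents do not give the share of subjects with no pain and no interference. Assume it is 5 to 30 percentage points higher on active than on placebo after baseline, with arms balanced at baseline and the *Very severe / Not at all* combination negligible.

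- Bodily Pain: 0.05 × 4.23 = 0.21 to 0.30 × 4.23 = 1.27 points understated
- PCS: 0.31754 × 0.21 = 0.07 to 0.31754 × 1.27 = 0.40 points understated

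**The case against.** The strongest reply is that Section 3.2.11 defers to the user's manual. The printed table can be read as a faulty transcription of it, and if the manual is what gets programmed, no score changes. That stands as a limit on the harm. It does not clear the SAP, which prints an explicit rule without saying that the manual overrides it. Someone programming or validating from the SAP would apply the printed rule.

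Several narrower points also stand.

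- Only the two *Not at all* columns are wrong. The values 4, 3, 2, 1 run the right way, and *Not at all* always outscores *A little bit*.
- The direction rule has one printed exception, item 2, but that item enters no domain score.
- The SAP's own text shows that the printed conditions are wrong. It does not by itself prove that 6 belongs to *None* alone, so the repair needs checking against the manual.
- The companion table supports 6 as the intended top of item 8, but it can never feed a score. Bodily Pain has two items, so a missing item 7 is half of them, and the missing-item rule then sets the domain to missing.
- The SAP nowhere prints 11 as a maximum. The item limits of 1 to 6 give 2 to 12, so 2 to 11 is the less natural reading and would arise only if a programmer took the maximum from the printed table.

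Finally, SF-36 is one of many secondary endpoints, and no trial conclusion is shown to change. That bears on priority. The table is still wrong.

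**Conclusion.** The recode is wrong as written, on the SAP's own direction rule and item 7 scale, and neither raw range rescues it. On range 2 to 12 the error falls mainly on subjects with no pain and no interference, who are the best pain responders. Each loses 4.2 norm-based Bodily Pain points and 1.3 PCS points and gains 0.4 MCS points. Under the assumed 5 to 30 point gap, the treatment difference would be understated by 0.2 to 1.3 points on Bodily Pain and 0.07 to 0.4 on PCS. All of this holds only if the printed table is programmed, which the documents do not settle. The primary endpoint and the interim stopping and arm-dropping rules do not use SF-36. It should be corrected because it is an explicit scoring rule for a listed major secondary endpoint and the repair is nearly free.

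**What to change.** In SAP Section 3.2.11.1:

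1. Exchange *None* and *Very severe* between the two *Not at all* columns, so that item 8 scores 6 when item 7 is *None* and 5 when it is *Very mild* to *Very severe*. Check this against the user's manual cited in Section 3.2.11.
2. State the Bodily Pain raw range as 2 to 12, and say which source governs if the table and the manual differ.
3. Reconcile the table for an unanswered item 7 with the rule that sets a domain to missing when half its items are missing.
4. Check the derivation program on three records: *None / Not at all* should give 100, *Very mild / Not at all* 84 and *Very severe / Not at all* 40. Together these detect the printed table on either range. With the range fixed at 2 to 12, also confirm that the program reproduces the PCS and MCS limits in Section 3.2.11.2.

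The cost is a short SAP correction and one check of the derived-dataset program. No data collection changes.

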### Quality of Life and Patient-Reported Outcomes

The questionnaires will be completed at relevant study visits as described in the Time and Events Table (Section 7.1), and the data will be directly entered into the ePRO.

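### The SF-36 missing-item rule deletes Bodily Pain or Social Functioning, and both summary scores, after one unanswered item, and leaves the SAP's item 8 values for a missing item 7 without effect

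*SAP*

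**What the plan says.** The SF-36 endpoint, listed among the major secondary efficacy endpoints in SAP section 2, is "Change from baseline in physical and mental component scores and in domain scores of SF-36 at all assessment timepoints".

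SAP 3.2.11.1 states the missing-item rule from both sides. First: "Domain scores will only be calculated if less than half of the item scores are missing". Then it gives the converse: with half or more of a domain's items unanswered, nothing is imputed and there is no domain score. Where imputation is allowed, "Missing item scores will be imputed as the mean of the other item scores within the same domain".

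The same section defines Bodily Pain as item 7 plus item 8, and Social Functioning as item 6 plus item 10. It also says "Item 8 is recoded depending on whether item 7 is answered or not", and gives a separate set of item 8 values for use when item 7 is NA: 6.0, 4.75, 3.5, 2.25 and 1.0.

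SAP 3.2.11.2 adds: "Component scale scores (PCS and MCS) will be set to missing if the subject is missing any one of the eight SF-36 scales". SAP 4.5.2.2 does not replace a missing baseline efficacy value, so the change from baseline is then missing at all visits.

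For the scoring source, SAP 3.2.11 says "Recoding, calculations and standardisation will be done as recommended in the User’s manual for the SF-36". On data capture, Protocol Appendix 12.7 says that "the data will be directly entered into the ePRO".

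**The concern.** For a two-item scale, exactly half missing means one item missing, and the SAP puts that case on the side where the domain is lost. One blank among the 35 scored items (36 less item 2, which enters no domain) can then remove 3 of the 10 reported SF-36 scores at that visit: the affected domain, PCS and MCS. A blank at baseline removes them for that subject throughout.

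The item 8 values for a missing item 7 suggest that this was not thought through. They serve a purpose only if Bodily Pain can be scored when item 7 is absent, and the missing-item rule never allows that. At stake is avoidable loss of usable answers on a listed major secondary endpoint.

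**Working it through.** **Inputs.** The item counts per domain come from the sums in SAP 3.2.11.1. The SAP rule calculates a domain of n items with m missing if m < n/2. The alternative calculates it if at least half of the items are answered, that is m ≤ n/2.

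**Step 1. Fewest missing items that delete each domain.**

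| Domain | n | SAP rule | Alternative |
|---|---|---|---|
| Bodily Pain | 2 | 1 | 2 |
| Social Functioning | 2 | 1 | 2 |
| Role Emotional | 3 | 2 | 2 |
| Role Physical | 4 | 2 | 3 |
| Vitality | 4 | 2 | 3 |
| General Health | 5 | 3 | 3 |
| Mental Health | 5 | 3 | 3 |
| Physical Functioning | 10 | 5 | 6 |

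Bodily Pain and Social Functioning are the only domains that one blank removes.

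**Step 2. Follow a missing item 7.** Item 8 is answered, so m = 1 and n/2 = 1. The condition m < n/2 fails and Bodily Pain is missing. Item 8 enters no other domain, so none of the five NA values reaches a domain score, PCS or MCS.

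Under the alternative rule, item 7 is imputed by the item 8 value v. The raw score is 2v and the 0–100 score is 100 × (2v − 2)/10:

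| Item 8 value | Raw score | 0–100 score |
|---|---|---|
| 6.0 | 12 | 100 |
| 4.75 | 9.5 | 75 |
| 3.5 | 7 | 50 |
| 2.25 | 4.5 | 25 |
| 1.0 | 2 | 0 |

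The printed values are evenly spaced (steps of 1.25) and cover the full Bodily Pain range, so the recode works as soon as the domain may be calculated.

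**Step 3. Size of the loss.** The documents give no item non-response rate and no loss figure to reproduce, so this step is illustrative. Assume that each item is skipped independently with probability q. A domain is calculated with probability Σ C(n,m) qᵐ(1−q)ⁿ⁻ᵐ over the allowed m. PCS and MCS are lost with probability 1 minus the product over the eight domains.

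At q = 1% under the SAP rule:
- Bodily Pain and Social Functioning together: 0.99⁴ = 0.96060, a loss of 3.94% from these four items alone.
- Role Physical and Vitality, each: 0.99⁴ + 4 × 0.01 × 0.99³ = 0.99941.
- Role Emotional: 0.99³ + 3 × 0.01 × 0.99² = 0.99970.
- The other three domains are close to 1.
- Product 0.9592, so the loss is 4.1%.

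| Assumed q per item | PCS/MCS lost, SAP rule | of which the four BP and SF items alone | PCS/MCS lost, alternative |
|---|---|---|---|
| 0.25% | 1.0% | 1.0% | 0.003% |
| 0.5% | 2.0% | 2.0% | 0.013% |
| 1% | 4.1% | 3.9% | 0.05% |
| 2% | 8.3% | 7.8% | 0.22% |

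If the ePRO does not allow an item to be skipped, q = 0 and the loss is nil under either rule.

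**The case against.** A reader might infer that the recode and the missing-item rule contradict each other, so that the score cannot be programmed. The documents do not support that. The recode assigns an item value and the missing-item rule decides whether a domain is calculated. Both can be followed as printed, and every response pattern has one result. The NA values are inert, not contradictory.

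A reader might also infer that about 4% of summary scores will be lost. That figure belongs to one assumed non-response rate. Neither document says whether the ePRO allows skipping, so the range starts at zero.

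Nor can it be said that the SAP departs from the SF-36 manual it cites. The manual was not available for this review, and nothing here rests on its content.

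The strict rule may also be deliberate. It is stated twice and consistently, and other scores in the SAP are strict: one missing component removes DAS28, SDAI or CDAI, and HAQ-DI needs six of eight areas. The SAP has no single convention, however: a joint count is lost only when more than half of the joints are missing (SAP 3.2.3).

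The consequence is limited too. A repeated-measures model uses a subject's other visits when a post-baseline score is missing, and no SF-36 result enters the interim decision criteria in SAP Table 4.

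All of this stands and keeps the point minor. It does not explain why the SAP prints item 8 values that its own rule never lets through.

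**Conclusion.** The point holds as a small flaw in the scoring rules. From the SAP text alone, one blank in Bodily Pain or Social Functioning removes that domain, PCS and MCS at the visit. At baseline it removes those changes for that subject at all visits. The item 8 values for a missing item 7 cannot influence any reported score, which shows that the two provisions were not reconciled. The documents do not settle which of them reflects the intention.

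The size is uncertain: nil with forced answers, and about 1% to 8% of PCS and MCS values at 0.25% to 2% non-response per item. That range rests on assumed rates and independent skipping. Under the alternative rule the loss is at most about 0.2% over the same rates.

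**What to change.** Preferred: amend the imputation paragraph of SAP 3.2.11.1 so that a domain is calculated when at least half of its items are answered, with missing items imputed by the mean of the answered ones, and is set to missing only when more than half are missing. The printed item 8 values for a missing item 7 then work without further change.

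The SAP should state two costs. A two-item scale may be scored from one answer, in effect that item doubled. The change also reaches beyond the two-item scales: the number of missing items that deletes a domain rises from 2 to 3 for Role Physical and Vitality, and from 5 to 6 for Physical Functioning.

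If the sponsor intends the strict rule, it should keep it and delete the unused item 8 values. Either way, the sponsor should check the choice against the cited manual, state whether the ePRO allows skipped items, and settle the rule before unblinding. The work is a short SAP edit and a line of code.
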